13.2. SUBSEQUENT ONCOLOGY THERAPY

Subsequent oncology therapies taken after end of treatment will be collected in below forms:

- “Oncology Medication (CHEMO1)”
- “Oncology Radiotherapy”
- “Oncology Surgery and Procedure”

Subsequent oncology therapies are defined as therapies started after the last dose of study medication. The following information will be summarized and listed for subsequent therapy:

- Number of subsequent oncology medications
- Number of subsequent regimen
- Category of number of subsequent regimen

Subsequent oncology (or anti-tumor) medications will also be presented by ATC level 2 and by PTs for each dose/ disease cohort in each phase.

Subsequent anti-tumor therapy will be flagged in the listing of oncology medication/ radiotherapy/ surgery.

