#### **Early discontinuation of study treatment will occur if any of the following criteria is met:**

1. Patient withdrawal of consent;
2. Intolerable toxicity;
3. Poor patient compliance;
4. Use of other antitumor treatment during the study;
5. Pregnancy occurred during the study treatment period;
6. Patient is lost to follow-up;

7. Treatment discontinuation is in the best interest of the patient based on the assessment of the investigator and the Sponsor.

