### **Objective Response Rate (ORR)**

The ORR is defined as the percentage of patients with at least one best overall response (BOR) of CR or PR according to RECIST Version 1.1. To be assigned a status of PR or CR, changes in tumor measurements must be confirmed by repeat assessments performed no less than 4 weeks after the criteria for response are first met.

The BOR in an individual patient according to the RECIST criteria is the best response recorded from the start of treatment until documented RECIST progression or the date of any further anticancer therapy, whichever comes first. In the case of a patients without documented progression or additional anticancer therapy, BOR is determined using all available visit up until the last evaluable visit response.

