6.3.5. MISSING OR INCOMPLETE DATE INFORMATION FOR EFFICACY DATA

When a partial new anticancer therapy starting date is reported, every effort will be made to identify the precedence relationship of starting date of new anticancer therapy relative to last dosing date of study drug and the date of disease progression (if happened). According to the confirmed precedence relationship, partial new anticancer therapy date will be imputed to the earliest possible date:

- Day will be imputed as 1 if year and month are known; month and day will be imputed as Jan 1st if only year is known.
- In rare case, if year and month of death date are known but the day is unknown, day will be imputed as 15. For example, if a patient is reported to die on Dec2017, the death date will be imputed as 15 Dec2017.

However, the imputed anticancer start date will be adjusted based on corresponding date in different scenario as shown below, the imputed date will be set to the date according to which it will be adjusted if the originally imputed date is earlier than the corresponding date:

- Adjust based on the date of first dose in case that anticancer therapy starts earlier than both last dosing date and disease progression.
- Adjust based on the last dosing date/the date of disease progression which occurs earlier in case that anticancer therapy is initiated after last dosing date but before disease progression date or vice versa.
- Adjust based on the last dosing date/the date of disease progression which occurs later in case that anticancer therapy is initiated after both last dosing and disease progression.

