16.1. PRIMARY EFFICACY VARIABLE(S) & DERIVATION(S)

16.1.1. BEST OVERALL RESPONSE (BOR)

BOR will be determined using time point responses (TPRs) up until the last evaluable TPR prior to or on the date of (i) disease progression as defined by RECIST Version 1.1 (Eisenhauer et al., 2009) or death; or (ii) withdrawal of consent; or (iii) receiving subsequent anti-cancer therapy, whichever is earlier.

The timing of an overall TPR will always be derived based on scan dates not response assessment dates. For a scheduled tumor scan assessment, it is expected that there may be a variation for the actual timing of scans among target, non-target, and new lesions. In assigning a date for the overall response assessment at a visit, the earliest date collected at that visit will be used. Within a grouped timepoint, if there are multiple assessments on different dates for the same target lesions, the last assessment will be used.

A patient's BOR will be determined based on [APPENDIX 3](#).

Document: [REDACTED]

Author: [REDACTED]

Version Number:

2.5

Version Date:

18Feb2022

Template No.: [REDACTED]

Reference: CS_WI_BS005

Effective Date: 02Dec2019

There are two ways of assigning BOR for a patient when the minimum interval for confirmation of CR and PR is not satisfied or if there are no confirmatory scans for CR and PR:

- Adding two more response categories as: unconfirmed CR, unconfirmed PR.
- Assigning BOR as SD, that is, both the unconfirmed CR and unconfirmed PR will be SD.

Both ways of assigning BOR will be implemented.

The number and percentage of patients in each category of derived BOR (Confirmed CR, Confirmed PR, SD, PD, or NE) will be summarized.

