16.1.5. PROGRESSION FREE SURVIVAL (PFS)

The PFS is defined as the time from date of first dosing until the date of an objective disease progression as defined by RECIST Version 1.1 (Eisenhauer et al., 2009) or death due to any cause, whichever comes first. More specifically, PFS will be determined using all the assessment data up until the last evaluable visit prior to or on

Document:	[REDACTED]		
Author:	[REDACTED]	Version Number:	2.5
		Version Date:	18Feb2022
Template No.:	[REDACTED]	Reference:	CS_WI_BS005
Effective Date:	02Dec2019		

the date of (i) disease progression as defined by RECIST Version 1.1 or death; or (ii) withdrawal of consent; or (iii) receiving subsequent anti-cancer therapy, whichever is earlier.

The rule of censoring/ event is summarized in Table 1.

The PFS time will always be derived based on scan dates not tumor assessment dates. If PD is documented between scheduled visits, the actual date of documented progression will be used as an uncensored value in the analysis of PFS.

RECIST assessments/scans contributing towards a particular visit may be performed on different dates. The following rules will be applied:

- Date of progression will be determined based on the earliest of the dates of the component that triggered the progression.
- When censoring a patient for PFS the patient will be censored at the latest of the dates contributing to a particular overall visit assessment.

Table 1 Progression free survival

Description	Event/ Censor	Date of Event/Censor
Documented progression before starting use of new anticancer treatment and without missing two consecutive tumor assessment visits	Event	Date of first documented disease progression
Death without progression	Event	Date of death
Progression or death after two or more consecutive missed tumor assessments	Censor	Date of last adequate tumor assessment before two consecutive missed tumor assessment visits
No evaluable baseline tumor assessment	Censor	Date of first dosing of study treatment
No evaluable tumor assessment after first dose of study treatment	Censor	Date of first dosing of study treatment
New anticancer treatment started prior to documented disease progression or death on study	Censor	Date of last evaluable tumor assessment before start use of new anticancer treatment/two consecutive missed tumor assessment visits
No progression and no death before end of study or data cut-off	Censor	Date of last evaluable tumor assessment

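### Read literally, SAP 16.1.1 with 13.2 keeps the best-overall-response period open after anticancer therapy begun on or before the last fruquintinib dose, whereas protocol 8.5 closes it

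*SAP*

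**What the plan says.** Protocol 8.5, under Objective Response Rate, takes the best response recorded "until documented RECIST progression or the date of any further anticancer therapy, whichever comes first". Nothing there depends on the date of the last dose.

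SAP 16.1.1 closes the same period at the earliest of progression or death, withdrawal of consent, or "receiving subsequent anti-cancer therapy, whichever is earlier". SAP 13.2 supplies the only definition: "Subsequent oncology therapies are defined as therapies started after the last dose of study medication". The SAP modification history for version 0.3 records that a definition of subsequent anti-cancer therapy was added, which is the term used in 16.1. SAP 2.4 mentions the added definition only as something the protocol lacked.

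The PFS text in SAP 16.1.5 limits the usable assessments with the same term: "ii) withdrawal of consent; or (iii) receiving subsequent anti-cancer therapy, whichever is earlier". Table 1 in that section censors on a different phrase: "New anticancer treatment started prior to documented disease progression or death on study". That row has no last-dose condition, and the PFS censoring rule in protocol 8.5 has none either.

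Both documents foresee other therapy during treatment. Protocol 3.6 lists, among the reasons for early discontinuation, "Use of other antitumor treatment during the study". SAP 6.3.5 has a date-imputation rule for the case where "anticancer therapy starts earlier than both last dosing date and disease progression".

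**The concern.** Protocol and SAP appear to use different stopping dates for the data behind BOR, ORR and DCR. If a programmer applies 13.2 to 16.1.1, an agent added while the patient is still taking fruquintinib does not qualify as subsequent. It does not come to qualify when fruquintinib stops either, because its start date stays on or before the last dose. Every later scan up to progression would then be eligible for BOR.

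At stake is attribution. In a single-arm cohort, a response that first appears after a second agent was added cannot be credited to fruquintinib, and protocol 8.5 excludes it. The same applies to stable disease when the second agent began before the scan that would qualify the patient for DCR. A reader of SAP 2.4 would not know that the rule had moved.

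Such a therapy also has no place in the descriptive tables. It is not prior, SAP 14 excludes oncology therapies from the concomitant category, and under 13.2 it is not subsequent.

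**Working it through.** No design figure is involved, so the check applies each rule to one patient and then sizes the effect.

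**Assumed patient.** Scans every 8 weeks, as for Cohorts C, D and E: day 57 SD, day 113 PR, day 169 PR, day 225 PD. Another anticancer therapy starts on day 100. The last fruquintinib dose is on day 110. All dates are hypothetical.

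| Rule | Does the day 100 start count? | Result |
|---|---|---|
| Protocol 8.5, BOR | Yes, any further therapy | Only day 57 is usable: BOR = SD |
| SAP 16.1.1 with 13.2 | No, because 100 is not after 110 | All scans are usable; the day 113 PR is confirmed at day 169: BOR = PR |
| SAP 16.1.5 text with 13.2 | No | PFS event at day 225 |
| SAP 16.1.5 Table 1 | Yes | PFS censored at day 57 |
| Protocol 8.5, PFS | Yes | PFS censored at day 57 |

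The two BOR rules give different answers, and no table in 16.1.1 settles which applies. For PFS, Table 1 and the protocol agree, and only the text differs.

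There is a knock-on effect for duration of response. SAP 16.1.3 takes its censoring from the PFS rules. With BOR read literally and Table 1 applied, this patient's response would start on day 113 and be censored on day 57, before it began.

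**DCR.** SAP 16.1.4 counts stable disease lasting 7 weeks, and Appendix 3 uses a 49-day minimum. The patient above already qualifies at day 57 (57 > 49), so DCR does not change. It would change only if the other therapy had begun before that scan.

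**Size.** Each reclassified patient shifts the rate by 100/n points:

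- n = 40 (Cohorts B and C): 100/40 = 2.5 points; two patients, 5.0 points.
- n = 15 (Cohorts D and E): 100/15 = 6.7 points; two patients, 13.3 points.

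These are not upper limits. ORR and DCR use the efficacy analysis set, which under SAP 4.4 requires a measurable lesion, whereas protocol inclusion criterion 7 admits patients with bone lesions only. A smaller n gives a larger shift.

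For scale, the exact Clopper-Pearson interval for 4/40 is 2.8% to 23.7%, which matches the 0.03 and 0.24 in protocol Table 16. With one more responder, 5/40, it becomes 4.2% to 26.8%.

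**The case against.** The strongest reply is that 13.2 was never meant to govern 16.1. It speaks of oncology therapies, 16.1 speaks of anti-cancer therapy, and there is no cross-reference, although the SAP cross-refers elsewhere when it carries a rule over. SAP 6.3.5 imputes dates for therapy begun before both the last dose and progression, under a heading on efficacy data. That has a purpose only if such starts affect efficacy derivations. Table 1 is introduced as the summary of the PFS rule, which suggests the authors treated the two phrases as equivalent.

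Much of this stands. It is good evidence of intent, and it settles PFS: a reader might infer that the primary endpoint has two competing censoring rules, but Table 1 is the operative one and matches the protocol. It does not settle BOR. The modification history attaches the added definition to the very term used in 16.1, no other definition exists, and 16.1.1 has no table to correct a literal reading. If 13.2 was meant only for summaries, the term that closes BOR is undefined and needs the same repair.

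A reader might also infer that every patient who stops fruquintinib because of other antitumor treatment is affected. Protocol 3.6 does not support that. Dosing is 3 weeks on and 1 week off, and protocol 5.2.1 provides for interruptions. An agent begun in an off-week or an interruption, with fruquintinib never resumed, starts after the last dose and is subsequent even under 13.2.

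**Conclusion.** The point holds for BOR and for the ORR and DCR derived from it. As written, SAP 16.1.1 with 13.2 departs from protocol 8.5 for anticancer therapy begun on or before the last dose, and SAP 2.4 does not declare it. For PFS it is a mismatch between text and table with a clear answer.

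The practical effect is probably small. Protocol 5.3.2 prohibits other cancer therapy, and its use is a reason to stop. For confirmed ORR to change, a patient must start another agent on or before the last dose, without progression, and then first reach a response that is confirmed at least 4 weeks later. The documents give no count of such patients, so nothing here shows that any reported rate would be inflated. The shifts of 2.5 and 6.7 points are per patient and assume that the efficacy analysis set equals the planned 40 or 15.

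The conclusion rests on reading 13.2 as the definition of the term in 16.1.1, which the text permits but does not state. This is a minor clarification, worth making because it removes a derivation that could go wrong unnoticed.

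**What to change.** - In SAP 16.1.1 and the 16.1.5 text, replace the word subsequent with the Table 1 term, and define it once: new anticancer therapy other than fruquintinib, started on or after the first dose, regardless of the date of the last dose. Use that term in Table 1 and 6.3.5 as well.
- State in 13.2 that its after-last-dose definition applies only to the descriptive tables and listings.
- Say in the same definition whether palliative radiation permitted by protocol 5.3.2 counts for the analysis. Fruquintinib may be resumed after it, so it can predate the last dose. Without a statement, the broader definition could end BOR or censor PFS at permitted radiation by default.
- Confirm that the CRF captures start dates of anticancer therapy begun during treatment. SAP 13.2 describes its forms as collecting therapy after the end of treatment.

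The cost is a few lines of SAP text, a matching line in the derivation specification, and one check of the CRF. No sample size, endpoint or visit changes.

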14. MEDICATIONS AND PROCEDURES

Medications and procedures information are recorded as following:

- Prior and concomitant medication information
- Prior and concomitant procedure information

Document: [REDACTED]

Author: [REDACTED] Version Number: 2.5
Version Date: 18Feb2022

Template No.: [REDACTED] Reference: CS_WI_BS005

Effective Date: 02Dec2019

‘Prior’ medications/procedures are medications/procedures which started prior to the first dose of study medication.

‘Concomitant’ medications/procedures except for oncology therapies are medications which ended on or after the date of first dose of study medication or were ongoing at the end of the study, and start no later than 37 days following last dose administration.

A medication may be both prior and concomitant if it meets 2 above-mentioned definitions.

14.1. PRIOR AND CONCOMITANT MEDICATION

Medications will be coded using World Health Organization Drug Dictionary Enhanced (WHO DDE), Versions SEP2020 or higher. See [section 6.3.3](#) for handling of partial dates for medications, in the case where it is not possible to define a medication as prior and concomitant, the medication will be classified by the worst case, i.e. concomitant.

Concomitant medications will be presented by ATC level 2 and by PTs for each dose and/ or disease cohort in each phase. ATC class and PT will be sorted in descending frequency of the total number of patients with at least one condition in the corresponding category, ATCs/PTs will be presented alphabetically for ATCs/PTs of the same total frequency.

Prior and concomitant medications will be presented in listings with flag to differentiate whether the medication is prior medication or concomitant medication.

14.2. CONCOMITANT PROCEDURES

Surgery and procedures will be coded using MedDRA Version 23.1 or higher. Concomitant procedures will be presented by SOC and PT for each dose and/ or disease cohort in each phase.

SOC and PT will be sorted in descending frequency of the total number of patients with at least one condition in the corresponding category, SOC/PTs will be presented alphabetically for SOC/PTs of the same total frequency. Prior and concomitant surgery will be listed and flagged like the listing of prior and concomitant medication.

15. STUDY MEDICATION EXPOSURE

Exposure to study medication and compliance will be presented for the SAS.

The planned treatment is given at either 3mg QD or 5mg QD in the corresponding study phase and dose and/ or disease cohort. In each 28-day cycle, a patient will take medication in the first 3 weeks followed by 1 week off treatment. Study drug administration and derived exposure information will be summarized and listed.

Document: [REDACTED]

Author: [REDACTED] Version Number: 2.5
Version Date: 18Feb2022

Template No.: [REDACTED] Reference: CS_WI_BS005

Effective Date: 02Dec2019

15.1. EXPOSURE TO STUDY MEDICATION

Below variables will be summarized:

- Number of cycle(s) received: the number of cycles in which at least one dose of Fruquintinib or placebo is taken. The number of cycles could be further categorized into:
 - 1, 2, 3, 4, 5, 6 and > 6
- Total duration of exposure (days)
- Cumulative dose (mg)
- Dose intensity (mg/day)
- Relative dose intensity (RDI, %): both continuous variable and categorical variable (< 50%; 50 - < 70%; 70 - < 90%; 90 - < 110%; ≥ 110%)
- Actual duration of study treatment (days)
- Percentage intended dose (PID)
- Number of patients with any dose modification (including both drug interruption, dose increase, and dose reduction)
- Frequency of dose modification: 0, 1, 2, 3, 4, 5, 6, >6
- Number of patients experienced drug interruption
- Frequency of drug interruptions: 0, 1, ≥ 2
- Number of patients with any dose reduction
- Reduction from 5mg to 4mg
- Reduction from 4mg to 3mg
- Frequency of dose reduction: 0, 1, 2

15.2. STUDY MEDICATION COMPLIANCE

The study medication compliance is quantified with relative dose (RD, %) of study medication. RD is calculated as the cumulative dose taken divided by the planned total dose in the corresponding period, expressed as a percentage, see [section 15.3](#) for more details. RDI (%) and RD (%) will be categorized as stated above in [Section 15.1](#).

15.3. DERIVATIONS

- Total duration of exposure (days) is calculated from the first dose date of study drug in Cycle 1 to the last dose date of study drug + 8 days or death date, whichever comes earlier if treatment is discontinued, or to the cut-off date. if treatment is still ongoing.
- Actual duration of exposure (days) = Sum of the days with study drug administered

Algorithms for calculating parameters relevant to the dose exposure and intensity are listed in Table below:

Document:	[REDACTED]		
Author:	[REDACTED]	Version Number:	2.5
		Version Date:	18Feb2022
Template No.:	[REDACTED]	Reference:	CS_WI_BS005
Effective Date:	02Dec2019		

Parameter	Description/ Formula [a]
Dosing schedule per protocol#	5 mg PO QD between Days 1 and Day 21, followed by 1-week off
Cumulative dose (mg) [b]	$\sum [5 \times (\text{all dispensed 5-mg tablets} - \text{total returned 5-mg tablets} - \text{total lost 5-mg tablets in a cycle}) + 1 \times (\text{all dispensed 1-mg tablets} - \text{total returned 1-mg tablets} - \text{total lost 1-mg tablets in a cycle})]$
Dose intensity (mg/day)	Cumulative dose (mg) / Total duration of exposure (day)
Relative dose intensity (RDI, %) #	$100 * [\text{Dose intensity (mg/day)} / (5 \times 21/28, \text{mg/day})]$
Relative Dose (RD, %) #	$100 * [\text{Cumulative dose (mg)} / (5 \times 21 \times \text{number of cycles received (mg)})]$
Percentage intended dose (PID, %) [c]	$100 * [(\text{total number of days with any recorded doses}) / \text{total duration of exposure (days)}]$

[a]In the study, there are the other dose level of "3mg QD" used.

[b]In the study, both 1-mg and 5-mg fruquintinib are provided for oral administration. When dose adjustment is required, 1-mg fruquintinib is always used. Before calculating the cumulative dose, total number of 1-mg and 5-mg tablets taken should be counted separately.

[c]Given the dose schedule of a 4-week cycle in the protocol, 3 weeks on/ 1 week off, the reference value is 0.75.

indicates 5 (mg) should be replaced with 3 (mg) for calculation in Cohort "3 mg QD".

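### SAP 15.3 misstates relative dose and relative dose intensity for patients whose exposure ends part-way through a cycle

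*SAP*

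**What the plan says.** SAP 15.3 gives the schedule as "5 mg PO QD between Days 1 and Day 21, followed by 1-week off", which is 105 mg per 28-day cycle. Total duration of exposure runs from the first dose to "the last dose date of study drug + 8 days or death date, whichever comes earlier if treatment is discontinued". For a patient who has not stopped, it simply ends at cut-off. Dose intensity is cumulative dose over that duration, and RDI compares it with 5 × 21/28 = 3.75 mg/day. In the 3 mg cohort, 5 is replaced by 3.

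SAP 15.2 makes RD the measure of compliance: "RD is calculated as the cumulative dose taken divided by the planned total dose in the corresponding period, expressed as a percentage". The formula in 15.3 divides instead by 5 × 21 × the number of cycles received. SAP 15.1 defines that number as "the number of cycles in which at least one dose of Fruquintinib or placebo is taken".

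RDI and RD are both reported in five bands: below 50%, 50 to below 70%, 70 to below 90%, 90 to below 110%, and 110% or more. The SAP does not say whether the duration counts both end days.

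**The concern.** A patient who takes every scheduled dose should score about 100% on a compliance measure, whenever and however exposure ends. Two features of 15.3 prevent this.

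- **RD.** One dose in a cycle adds a full 105 mg to the denominator. The words in 15.2 and the formula in 15.3 give different answers whenever dosing in the last cycle ends before Day 21.
- **RDI.** The benchmark of 3.75 mg/day assumes three dosing weeks and one rest week. The duration includes a rest week for every patient who discontinues alive, even after a mid-cycle stop. It includes none for a patient who dies on drug or is still in the dosing weeks at cut-off.

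The error therefore depends on the exit route and its timing. Early stops can look like poor compliance, and ongoing or dying patients can look overdosed. Mid-cycle stops are foreseeable: Protocol 3.6 lists intolerable toxicity and withdrawal of consent among the reasons for early discontinuation. Cohorts are small (6 patients in A, 15 each in D and E, Protocol 8.6), so one misplaced patient moves a band by 1/6 = 17 or 1/15 = 7 percentage points. SAP 3 also allows analysis of accrued cohort data before the final analysis, when ongoing patients may have short exposure.

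**Working it through.** **Inputs (SAP 15.1 and 15.3).** 5 mg on Days 1–21 of 28; duration rules and 3.75 mg/day as above; 105 mg for each cycle started. The patient takes every scheduled dose, and treatment is discontinued (not merely held) on the day of the last dose. For exposure ending in Cycle k on Day d ≤ 21:

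- cumulative dose = 105(k − 1) + 5d
- duration by date subtraction = 28(k − 1) + d + 7 if discontinued alive; 28(k − 1) + d − 1 if death falls on the last dose day or the patient is ongoing at cut-off. An inclusive count adds 1.
- RDI = (dose/duration)/3.75; RD = dose/(105k)

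**The plan's own reference.** Last dose on Cycle 1 Day 21: duration 21 + 7 = 28 days; 21/28 = 0.75, the reference that 15.3 gives for percentage intended dose. RDI = 105/28/3.75 = 100% and RD = 105/105 = 100%. Subtraction therefore reproduces the plan. An inclusive count gives 29 days and RDI 96.6%.

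**Fully compliant patients** (RDI by subtraction, then inclusive):

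| Exposure ends | Dose (mg) | Days | RDI | RD |
|---|---|---|---|---|
| Stop alive, Cycle 1 Day 7 | 35 | 14 / 15 | 66.7% / 62.2% | 35/105 = 33.3% |
| Stop alive, Cycle 1 Day 14 | 70 | 21 / 22 | 88.9% / 84.8% | 70/105 = 66.7% |
| Stop alive, two cycles plus one dose | 215 | 64 / 65 | 89.6% / 88.2% | 215/315 = 68.3% |
| Death, Cycle 1 Day 14 | 70 | 13 / 14 | 143.6% / 133.3% | 66.7% |
| Ongoing, Cycle 2 Day 14 | 175 | 41 / 42 | 113.8% / 111.1% | 175/210 = 83.3% |
| Ongoing, Cycle 2 Day 21 | 210 | 48 / 49 | 116.7% / 114.3% | 100% |

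Under either day count, the death and both ongoing cases fall in the 110%-or-more band with no extra dose taken. Among Cycle 1 stops alive, RDI (by subtraction) is below 90% for Days 1–14 and RD for Days 1–18.

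**Longer exposure.** The lowest RDI for a stop alive (by subtraction) is 81.5% in Cycle 2, 89.6% in Cycle 3 and 92.8% in Cycle 4. The highest RDI for an ongoing patient in Cycle 4 is 107.7%, and at Cycle 14 Day 21 it is 102.1%. RD recovers more slowly: its minimum is 76.2% in Cycle 4 and 84.1% in Cycle 6.

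**Where the formulas work.** A patient ongoing on Day 28 of Cycle 1 has RD 100% and RDI 103.7% by subtraction or 100.0% inclusive.

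**The case against.** Several points on the other side carry weight.

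- **The 8 days are a consistent convention.** SAP Appendix 4 closes the last cycle on Day 7 after the last dose, and SAP 5.4 opens the post-treatment window at last dose + 8 days. This explains the rule, but not why it is paired with a full-cycle benchmark after a mid-cycle stop.
- **15.2 is a summary that points to 15.3**, and its period could mean the cycles received. Even so, the patient who stops on Cycle 1 Day 7 is charged for 14 doses not due after discontinuation, which is not compliance.
- **Importance is limited.** A reader might infer that RDI is the trial's tolerability measure at the recommended dose. The documents do not say so: Protocol 2.1.2 bases safety and tolerability on adverse events, no hypothesis is tested (SAP 5.5), and no decision rule uses RD or RDI. Reasons for discontinuation, and events leading to interruption, reduction or discontinuation, are reported directly.
- **The size is easily overstated.** A reader might conclude that the formulas are right only for a Day 21 stop, or that compliant patients range from 33% to over 140% on one scale. Neither is supported. Patients ongoing in the rest week can score 100%. The 33% is RD, while values above 100% are RDI only, and those above 140% need Cycle 1 exposure and date subtraction; an inclusive count caps at 133.3%. Scans fall on Day 1 of a cycle (Protocol 6.4), so many progression stops would have Day 21 as last dose. Under the one-year criterion in SAP 3, absent early termination, ongoing patients would be near 102%.
- **The obvious repair would do harm.** Ending the planned dose at the last dose hides lost drug. Take dosing on Days 1–7, a toxicity hold to Day 21, then discontinuation: SAP RD is 35/105 = 33%, but that repair gives 35/35 = 100%. Likewise, two full cycles with the second 14 days late give SAP RDI 210/70/3.75 = 80%, but counting only Days 1–21 of each started cycle gives 210/210 = 100%. This objection stands and shapes the fix.

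**Conclusion.** The point holds for exposure that ends part-way through a cycle. RD is too low whenever the last cycle's dosing ends before Day 21, and this does not depend on the day count. RDI is too low after a mid-cycle stop alive, and too high after death on drug or for patients still in the dosing weeks at cut-off. Compliant patients can land in the wrong band. The error is large in Cycle 1 and moderate in Cycle 2; by subtraction, RDI is within about 8 points of 100% from Cycle 4, while RD stays affected for longer.

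The figures assume full compliance at the starting dose and discontinuation dated to the last dose day. The percentages are the same at 3 mg. The share of patients affected cannot be derived from the documents. No inference about efficacy is touched, but the reported values would be wrong and the correction is cheap, so it should be made.

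**What to change.** 1. **RD.** Count 21 planned dosing days for each completed cycle. For the final cycle, count only the scheduled dosing days up to treatment discontinuation (a date already listed under SAP 8.2), death or cut-off. A hold before discontinuation then still counts as missed dose: the Days 1–7 example with discontinuation on Day 21 stays at 35/105 = 33%.
2. **RDI.** Keep calendar time, but divide the cumulative dose by the mg planned on the three-weeks-on, one-week-off calendar from first dose to that same end date. This replaces the fixed 3.75 mg/day over last dose + 8 days. Delays still lower RDI: with the second cycle 14 days late and exposure ending on study Day 63, the calendar plans 21 + 21 + 7 = 49 doses, so RDI = 210/245 = 86% while RD = 210/210 = 100%. The two measures stay distinct.
3. **Day count.** State whether it is inclusive, and whether the discontinuation day counts as a planned dosing day. For a last dose on Cycle 1 Day 7 with discontinuation dated Day 8, RD is 35/40 = 87.5% if that day counts and 100% if not.

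Under items 1 and 2, every compliant case in the table returns 100% when the end date is the last day shown; for example, Cycle 2 Day 14 is 175/(5 × 35). The cost is SAP text and programming only, with no new data.
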